11.4.4.2 Analyses of secondary efficacy endpoints

Descriptive statistics (number, mean, standard deviation, median, minimum, and maximum) will be provided by treatment for all continuous secondary variables defined in [Section 9.2.1](#) at the scheduled visits for the 26-week randomized treatment period. For continuous variables in the extension period defined in [Section 9.2.1](#), descriptive statistics will be provided for FRC group at the scheduled visits for the whole study period including the extension period.

Except for 2-hour PPG and glucose excursion, all continuous secondary efficacy endpoints at Week 26 defined in [Section 9.2.1](#) will be analyzed using the same MMRM approach as described in [Section 11.4.4.1](#) to compare FRC with GLP-1 receptor agonist. This model will include fixed effect terms including treatment group (FRC or GLP-1 receptor agonist), randomization strata of HbA1c (<8%, \geq 8%) at V1 (Week -2), randomization strata of GLP-1 receptor agonist subtype (once/twice daily formulations, once weekly formulations) at screening, scheduled visit, treatment-by-visit interaction, and world region, and the covariate of baseline value-by-visit interaction. Means and adjusted means of each treatment group will be provided, as well as adjusted mean and associated two-sided 95% CI of the differences between treatment groups. The statistical tests for between-group differences will be two-sided at the alpha level of 0.05. The analyses include all scheduled measurements collected during the 26-week randomized treatment period including those obtained after IMP discontinuation or rescue medication use.

2-hour PPG and glucose excursion, for which only one post baseline measurement is scheduled, will be analyzed using the similar ANCOVA with the missing data at Week 26 imputed by LOCF as described in [Section 11.4.4.1](#) to compare FRC with GLP-1 receptor agonist. This model will include fixed effect terms including treatment group (FRC or GLP-1 receptor agonist), randomization strata of HbA1c (<8%, \geq 8%) at V1 (Week -2), randomization strata of GLP-1 receptor agonist subtype (once/twice daily formulations, once weekly formulations) at screening, and world region, and a covariate using the corresponding baseline value. Means and adjusted means of each treatment group will be provided, as well as adjusted mean and associated two-

sided 95% CI of the difference between treatment groups. The LOCF procedure will be used by taking the last available post-baseline collected during the 26-week randomized treatment period as the value at Week 26.

All categorical secondary efficacy endpoints defined for the 26-week randomized treatment period in [Section 9.2.1](#) will be analyzed using a Cochran-Mantel-Haenszel (CMH) method stratified on randomization strata of HbA1c (<8%, ≥8%) and randomization strata of GLP-1 receptor agonist subtype (once/twice daily formulations, once weekly formulations) at screening visit (V1, Week -2). The proportion in each treatment group will be provided, as well as the difference of proportions between groups with associated 2-sided 95% CI. For the categorical secondary endpoints in which HbA1c is assessed at Week 26, all values at Week 26 will be used to determine whether a patient is a responder or not, even if they are measured after IMP discontinuation or introduction or rescue therapy. If no assessment is available at Week 26 at all, patients will be treated as failures (non-responders).—For the categorical secondary endpoints defined for the extension period in [Section 9.2.1](#), counts and percentages will be summarized using all data available at Week 52, with patients having data missing at Week 52 treated as non-responders.

11.4.4.3 Multiplicity considerations

[figure not shown]
To control the type I error, a step-down testing procedure (please see [Figure 1](#)) will be applied.

For the primary efficacy endpoint (change from baseline to Week 26 in HbA1c), no multiplicity adjustment is needed to control the Type I error since only one comparison of FRC versus GLP-1 receptor agonist will be performed.

If the primary variable is statistically significant at the 5% level, a hierarchical testing procedure will be performed to test the following secondary efficacy variables in the following prioritized order. Testing will stop when an endpoint is found not to be statistically significant at the 5% level:

1. Percentage of patients reaching HbA1c <7% at Week 26.
2. Change in FPG from baseline to Week 26.
3. Change in the daily average of the 7-point SMPG from baseline to Week 26.
4. Change in 2-hour Post Prandial Glucose (PPG) and/or glucose excursion during the standardized meal test from baseline to Week 26.

Figure 1 - The step-down testing procedure

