7.2.1 Exclusion criteria related to study methodology

- E 01. At screening visit, age under legal age of adulthood;
- E 02. At screening visit, HbA1c <7% (53 mmol/mol) and >9% (75 mmol/mol);
- E 03. At screening visit, Body Mass Index (BMI) ≤ 20 or >40 kg/m²;
- E 04. History of hypoglycemia unawareness;
- E 05. History of metabolic acidosis, including diabetic ketoacidosis within 1 year prior to screening visit;
- E 06. Any use of anti-diabetic drugs within 3 months prior to screening visit (V1) other than those described in I 02;
- E 07. Previous treatment with insulin in the year prior to screening visit (V1) (note: short term treatment with insulin (≤ 10 days) due to intercurrent illness including gestational diabetes is allowed at the discretion of the study physician);
- E 08. Use of systemic glucocorticoids (excluding topical and inhaled forms) for a total duration of 10 days or more within 3 months prior to screening visit;
- E 09. Use of weight loss drugs within 3 months prior to screening visit; or any history of bariatric surgery;
- E 10. Use of any investigational drug within 1 month or 5 half-lives, whichever is longer, prior to screening visit;
- E 11. Personal or immediate family history of medullary thyroid cancer (MTC) or genetic conditions that predispose to MTC (eg, multiple endocrine neoplasia type 2 syndromes);
- E 12. Within the last 6 months prior to screening visit: history of stroke, myocardial infarction, unstable angina, or heart failure requiring hospitalization;
- E 13. Planned coronary, carotid or peripheral artery revascularization procedures to be performed during the study period;
- E 14. Known history of drug or alcohol abuse within 6 months prior to the time of screening visit;
- E 15. Uncontrolled or inadequately controlled hypertension (systolic blood pressure >180 mmHg or diastolic blood pressure >95 mmHg) at screening visit (V1);

E 16. Conditions/situations such as:

- Patients with conditions/concomitant diseases making them non evaluable for the primary efficacy endpoint (eg, hemoglobinopathy or hemolytic anemia, receipt of blood or plasma products within the last 3 months prior to the screening visit);

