The baseline value for efficacy endpoints is the last available value prior to the first injection of open-label IMP or the last available value on or before the date of randomization if not treated with open-label IMP.

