Summary statistics (for screening value, baseline value, observed values, and observed changes from baseline) at scheduled visits (using OC) will be provided for each treatment group for continuous secondary efficacy endpoints. Each summary will include the number of observations, mean, SD, SE, minimum, median, and maximum. Graphical presentations will also be used to examine trends over time using mean values (±SE) and mean changes from baseline (±SE) at each of the scheduled visits (using OC).

All categorical secondary efficacy endpoints defined for 26-week randomized treatment period in [Section 2.1.3.2](#) will be analyzed using a Cochran-Mantel-Haenszel (CMH) method stratified on randomization strata of HbA_{1c} (<8%, ≥8%) at visit 1(week -2) and randomization strata of GLP-1 receptor agonist subtype (QD/BID formulations, QW formulations) at screening. The proportion in each treatment group will be provided, as well as the difference of proportions between groups

with associated 2-sided 95% CI. For the categorical secondary endpoints in which HbA1c is assessed at Week 26, all values at Week 26 will be used to determine whether a patient is a responder or not, even if they are measured after IMP discontinuation or introduction or rescue therapy. If no assessment is available at Week 26 at all, patients will be treated as failures (non-responders).

For HbA1c responders ($\leq 6.5\%$, $< 7\%$), summary tables and graphs will be provided by treatment group at scheduled visits (using OC). For between-group comparison, a sensitivity analysis will be performed excluding patients whose HbA1c values at baseline are $\leq 6.5\%$ (for the $\leq 6.5\%$ responder analysis) or $< 7\%$ (for the 7% responder analysis). The summary by visit may also be provided excluding those patients.

A KM curve will be provided by treatment group for the cumulative incidence of rescue therapy during the 26-week randomized treatment period and during the whole study period including the extension period (FRC group only). A listing will be provided for rescued patients.

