Week 18 (Visit 24)	127	106 to 140
Week 22 (Visit 26)	155	141 to 168
Week 26 (Visit 28)	183	169 to 210 (for patients who are eligible to enter the extension period)
		169 to . (for patients who are not eligible to enter the extension period)

Study days are calculated from the day of first IMP injection; the day of first IMP injection is Day 1.

The analysis windows for other parameters analyzed by MMRM can be obtained similarly based on their respective scheduled visits. After applying these time windows, if multiple assessments are associated to the same time point, the closest from the targeted study day will be used. In case of equality, the earliest measurement will be used.

Reference day

The reference day for the calculation of extent of exposure, time to onset, and relative days will be the day of the first injection of open-label IMP, denoted as Day 1.

Baseline definition for efficacy/safety data

For the safety analyses, the baseline for a given parameter is defined as the last available measurement, including unscheduled assessment, assessed prior to the first injection of open-label IMP. For the efficacy analyses, the baseline for a given parameter is defined as the last available measurement, including unscheduled assessments, assessed prior to the first injection of open-label IMP or the last available value on or before the date of randomization if not treated with open-label IMP.

Efficacy endpoints at Week 26

Efficacy endpoints at Week 26 will be assessed using values measured at Visit 28 (Week 26). For ANCOVA-LOCF approach, if a patient discontinues the treatment prematurely, received rescue therapy, or does not have a measurement at Visit 28 for efficacy endpoints, the last non-missing post-baseline value, including measurements from unscheduled visits will be used as the value at Week 26.

Summary statistics by visit for continuous efficacy endpoints

Summary statistics (N, mean, SD, SE, minimum, median, maximum) of continuous efficacy endpoints (observed data and change from baseline) will be provided at scheduled visits as per protocol. Summaries showing data by visit will be presented according to the visit number (or re-allocated visit number) and labeled with the targeted approximate day/week.

Last on-treatment value for laboratory variables and vital signs

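### The first gated secondary test (HbA1c <7% at Week 26) adjusts for starting HbA1c only through a cut at 8%, giving up a little precision that continuous baseline HbA1c would recover

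*Protocol*

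**What the plan says.** **Entry.** Protocol 7.2.1 excludes patients by "At screening visit, HbA1c <7% (53 mmol/mol) and >9% (75 mmol/mol" and Protocol 10.1.2.1 gives the eligible range as 7% to 9% inclusive, so a screening value of exactly 7.0% qualifies.

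**Baseline.** HbA1c is drawn again at V3. Protocol 9.2.1 states: "The baseline value for efficacy endpoints is the last available value prior to the first injection of open-label IMP". Baseline can therefore differ from the screening value that sets the stratum.

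**Endpoint.** Step 1 of the hierarchy is "Percentage of patients reaching HbA1c <7% at Week 26". SAP 2.5.4 adds: "Efficacy endpoints at Week 26 will be assessed using values measured at Visit 28 (Week 26". A missing Week 26 value counts against the patient: "If no assessment is available at Week 26 at all, patients will be treated as failures (non-responders" (Protocol 11.4.4.2).

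**Test.** The categorical endpoints "will be analyzed using a Cochran-Mantel-Haenszel (CMH) method stratified on randomization strata of HbA1c (<8%, ≥8"%, and also on GLP-1 RA subtype (Protocol 11.4.4.2; SAP 2.4.4.2 is the same). Neither a continuous baseline HbA1c nor world region enters.

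**Other efficacy models.** The primary MMRM (Protocol 11.4.4.1, SAP 2.4.4.1), the MMRMs for continuous secondary endpoints and the meal-test ANCOVA (Protocol 11.4.4.2, SAP 2.4.4.2) all include a continuous baseline value and world region.

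**Sensitivity analysis.** For the responder endpoints, SAP 2.4.4.2 says "a sensitivity analysis will be performed excluding patients whose HbA1c values at baseline are" already at target (≤6.5% or <7%, according to the endpoint).

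**The concern.** For an endpoint defined by crossing 7%, the starting distance from 7% is an obvious prognostic variable. Entry runs from 7.0% to 9.0%, and the only adjustment is one cut at 8%. Within the lower stratum, a patient at 7.0% needs almost no fall to reach target and a patient at 7.9% needs nearly a full point. The planned test does not use that difference.

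What is at stake is efficiency. This step gates FPG, the 7-point SMPG average and the meal-test endpoint: if it misses 5%, formal testing stops. The protocol states no power for it. The missing covariate is already collected and is used in the primary model, so the loss is avoidable.

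**Working it through.** **1. Reproduce the plan's sample size.** Inputs from Protocol 11.1: SD 1.1%, difference 0.4%, 20% drop-out with FRC drop-outs responding as control, two-sided 5%, at least 90% power. Diluted effect = 0.8 × 0.4 = 0.32%.

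n per arm = 2 × (1.960 + 1.282)² × 1.1² / 0.32² = 248.3, so 249 by the normal approximation. The exact t-test gives 250, with power 90.1%. The plan's 250 per group reproduces.

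**2. How coarse is the 8% cut?** Assume no mean change and values reported to 0.1%. The chance that a patient starting at b reads below 7% is Φ((6.95 − b)/SD), where SD is that of individual change. Only 1.1 is in the plan; 0.5 is an assumption.

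| Start | Stratum | SD 0.5 | SD 1.1 |
|---|---|---|---|
| 7.0% | <8% | 46% | 48% |
| 7.5% | <8% | 14% | 31% |
| 7.9% | <8% | 3% | 19% |
| 8.0% | ≥8% | 2% | 17% |

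At SD 1.1, for example, the 7.9% row is Φ(−0.95/1.1) = Φ(−0.864) = 0.19. At either SD, almost all of the prognostic spread between 7.0% and 8.0% lies inside the lower stratum, and crossing the cut from 7.9% to 8.0% changes little.

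**3. What that costs.** Simulation: 250 per arm, 3,000 trials per setting, randomised within the four strata, planned CMH compared with logistic regression on continuous HbA1c. Assumptions not in the documents: starting HbA1c uniform on 7–9% or truncated normal (mean 7.8, SD 0.6); SD of change below 1.1; screening value used as baseline. Missing Week 26 values were not simulated separately; drop-out enters only through the 0.32% effect.

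*Type I error:* CMH 4.4% to 5.6%, logistic 4.3% to 5.6% (Monte Carlo error about 0.4 points). Both hold the 5% level.

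*Power at 0.32%, no mean change in control:*

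| SD of change | Uniform: CMH → logistic | Truncated normal: CMH → logistic |
|---|---|---|
| 1.1 (plan) | 59% → 60% | 64% → 65% |
| 0.8 | 77% → 80% | 82% → 84% |
| 0.5 | 92% → 95% | 95% → 97% |

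With a control change of −0.4%, the gains are also within 0 to 3 points. A larger gain, 73% to 84%, appeared only at an effect of 0.2% with SD 0.3, which is not the plan's scenario. At SD 0.3 and the 0.32% effect, CMH power is already 98% or more.

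*Variance of the risk difference:* the standardised logistic estimate had about 3% to 4% lower variance than the stratified difference near SD 1.1, rising to about 15% lower at SD 0.5. As standard errors: √0.97 = 0.985 and √0.85 = 0.922, so about 1.5% to 8% smaller.

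**The case against.** The strongest reply is that nothing is broken. Randomisation protects the null, CMH keeps its 5% level and matches the stratified randomisation, and the 8% cut does adjust to some degree. At the plan's own SD the gain is about 1 power point. A model-based difference replaces a nearly assumption-free one. The SAP also already drops patients below 7% at baseline in a sensitivity analysis, and the primary test, which must succeed first, uses continuous baseline HbA1c. All of this stands, and it keeps the point minor. What remains is that the planned exclusion does not adjust for distance among patients just above 7%, and that an available covariate is left unused at the step gating three others.

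A reader might go further and infer that the responder percentages are wrongly inflated, because a patient admitted at 7.0% can fall below 7% by chance. The documents do not support that. The stated objective is the percentage reaching target, not a change caused by treatment in each patient, and both arms' proportions are reported with their difference. Chance crossing occurs in both randomised arms. Applying the SD of 1.1% with zero mean change gives about 20% to 22% responders in the simulation, but that SD describes 26-week change and includes real individual change. It cannot be read as measurement noise.

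**Conclusion.** The point holds as a minor matter of precision. The step-1 test adjusts only coarsely for distance from the 7% target, unlike the primary and continuous secondary analyses. The size is roughly a 3% to 15% reduction in the variance of the risk difference forgone (SD of change 1.1 down to 0.5), and 0 to 3 power points at the 0.32% diluted effect, about 1 point at SD 1.1. These figures rest on the assumed baseline distributions and SDs of change. Patients counted as failures for missing data would probably shrink the gain, since baseline HbA1c need not predict missingness.

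The planned test is valid, the hierarchy is sound, and nothing here calls for changing the 7% target or requiring a confirmed response. A reader should not conclude that a step-1 result under the current plan would be wrong.

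**What to change.** In SAP 2.4.4.2 and Protocol 11.4.4.2, analyse HbA1c <7% and ≤6.5% at Week 26 with a logistic model containing treatment, the two randomisation strata, world region and continuous baseline HbA1c. Report the standardised (marginal) difference in proportions with its 95% CI, and state which p-value counts at step 1. Keep the missing-as-failure rule and the sensitivity analysis excluding patients already at target. Retain the stratified CMH as supportive.

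If the sponsor prefers CMH as the confirmatory test, prespecify the logistic analysis as supportive instead. In either case, settle the choice before the Week 26 database lock.

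The cost is wording and one additional model, with no new data. The small downside is that the adjusted difference is model-based.

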11.4.5 Analyses of other endpoints

Analyses of other endpoints defined in [Section 9.3](#) will be performed on the mITT population using all assessments obtained during the 26-week randomized treatment period, including those obtained after IMP discontinuation or introduction of rescue therapy. The similar analyses will also be performed using assessment obtained during 26-week on-treatment period (see [Section 9.2](#)), unless otherwise specified. Descriptive statistics will be summarized by treatment group. For selected other endpoints defined in [Section 9.3.2](#), descriptive statistics will also be summarized for FRC group for the whole study period including the extension period.

For PK parameters, lixisenatide total plasma concentrations will be listed and summarized by visit and time window and by anti-lixisenatide antibody status in the PK population, using descriptive statistics by N, geometric mean, coefficient of variation, median, minimum and maximum. The results of the PK evaluation and the immunogenicity assessments will be issued separately from the study report.

11.4.6 Analyses of safety data

See [Section 9.2.2](#).

The summary of safety results will be presented by treatment group for the 26-week randomized treatment period, unless specified otherwise. Similar summary of safety results will also be presented for FRC group for the whole study period including the extension period, as appropriate.

All safety analyses will be performed on the safety population as defined in [Section 11.3.2](#) using the following common rules:

The baseline value is defined as the last available value prior to the first injection of open-label IMP.

The following definitions will be applied to laboratory parameters and vital signs.

- The potentially clinically significant abnormality (PCSA) values for clinical laboratory tests and vital signs are defined as abnormal values considered medically important by Sponsor's Global Pharmacovigilance and Epidemiology department and in effect at the time of the final SAP approval. PCSA criteria for parameters not cited in the protocol as safety parameters will not be analyzed;
- PCSA criteria will determine which patients had at least 1 PCSA during the on-treatment period, taking into account all evaluations performed during the on-treatment period, including unscheduled or repeated evaluations. The number of all such patients will be the numerator for the on-treatment PCSA percentage.

The "observation period" defined in [Section 9.2.1.1](#) are applicable for classification of symptomatic hypoglycemia, AEs, determination of on-treatment PCSA values and the last on-treatment value for the laboratory, vital sign and ECG parameters.

11.4.6.1 Analyses of symptomatic hypoglycemia

See [Section 10.6.1](#).

The number (%) of patients and event rate in patient years (2 types: the number of patients with events or the total number of events per 100 patient-year) of each type of symptomatic hypoglycemia (severe, documented and probable symptomatic hypoglycemia) will be summarized by treatment group. The pattern of symptomatic hypoglycemia occurrence over time will also be assessed, as appropriate.

11.4.6.2 Analyses of adverse events

Pre-treatment AEs are AEs that developed or worsened or became serious pre-treatment period.

Treatment-emergent AEs (TEAEs) are AEs that developed or worsened (according to the Investigator's opinion) or became serious during the period from the administration of first dose of the study treatments up to 3 days (9 days for the weekly GLP1) after the last administration..

Post-treatment AEs are AEs that developed or worsened or became serious during the post-treatment period.

The primary focus of AE reporting in the CSR will be on TEAEs. Pre- and post-treatment AEs will be described separately.

All adverse events

Adverse event incidence tables will present by system organ class (SOC) (sorted by internationally agreed order), high-level group term (HLGT), high level term (HLT) and preferred term (PT) sorted in alphabetical order for each treatment group, the number (n) and percentage (%) of patients experiencing an AE. Multiple occurrences of the same event in the same patient will be counted only once in the tables within a treatment phase. The denominator for computation of percentages is the safety population within each treatment group.

Summaries of all TEAEs in each treatment group will include:

- The overview of AEs, summarizing number (%) of patients with any
 - TEAE;
 - serious TEAE;
 - TEAE leading to death;
 - TEAE leading to permanent treatment discontinuation;
- The number (n) and percentage (%) of patients with at least one AE by primary SOC, HLGT, HLT and PT;
- Summary of TEAEs by maximal severity (severe, moderate, mild), presented by primary SOC and PT;
- Summary of TEAEs possibly related to open-label IMP, presented by primary SOC and PT.

A detailed listing of TEAE summaries will be provided in the statistical analysis plan.

Death and serious adverse events

Death and treatment-emergent SAEs will be summarized and presented as number and percent of patients in each treatment group.

The following deaths summaries will be generated:

- Number (%) of patients who died by study period (TEAE, on-study) summarized on the safety population by treatment received;
- Death in nonrandomized or randomized and not treated patients;
- TEAE leading to death (death as an outcome on the AE e-CRF page as reported by the Investigator) by primary SOC, HLGT, HLT and PT showing number (%) of patients sorted by internationally agreed order of SOC and alphabetic order of HLGT, HLT, and PT.

Adverse events leading to permanent treatment discontinuation

TEAEs leading to permanent treatment discontinuation will be summarized and presented as number and percent of patients in each treatment group.

Local tolerability at injection site

AEs related to local intolerability at the injection site will be identified by searching the term “injection site” in either the PTs coded from the Investigator reported terms or the PTs coded from the ARAC diagnosis terms. The number (%) of patients with related events will be summarized by treatment group.

Allergic reactions

The number (%) of patients with events adjudicated as allergic reactions by ARAC and with events adjudicated by ARAC as possibly related to the IMP will be summarized by treatment group. All the allergic events reported by the Investigators on the AE form for suspected allergic event and its associated complementary forms (confirmed or not confirmed by ARAC) will be listed.

Pancreatic-related events

- Increased pancreatic enzymes >2 times ULN
 - The number (%) of patients with events reported on the AE form for increased lipase and/or amylase >2 times ULN and its associated complementary forms will be summarized by PTs for each treatment group, sorted by decreasing incidence of PT.
 - The number (%) of patients with events positively adjudicated as pancreatitis by the PSAC will be summarized by type: 1) acute pancreatitis, 2) acute exacerbation of chronic pancreatitis, 3) chronic pancreatitis, 4) unknown pancreatitis. All events sent to PSAC for adjudication of pancreatitis (ie, events reported on the AE form for increased lipase and/or amylase >2 times ULN) will be listed along with the adjudication outcome.
- Pancreatic neoplasm
 - All the events sent to PSAC for adjudication for pancreatic neoplasm will be listed along with the adjudication outcome including PSAC diagnosis, type of neoplasm (malignant, benign, not determined), cancer stage and causal relationship to the study drug (related, possibly related, unlikely related, not related), etc.

Increased calcitonin

The number (%) of patients with events reported on the AE form for increased calcitonin ≥ 20 pg/mL and its associated complementary forms will be summarized by PTs for each treatment group.

ALT increase

The number (%) of patients with events reported on the AE form for ALT increase and its associated complementary forms will be summarized by PT for each treatment group.

Device-related events

The number (%) of patients with events reported on Device-related event questionnaire will be summarized for each treatment group along with 2 subcategories, events associated with a clinical event (either symptomatic hypoglycemic event or adverse event) and events not associated with clinical event. The number of events and rates in patient year will also be summarized as appropriate. In addition, a listing of patients with those events will be provided.

